# 1 INTRODUCTION

---

**Study title: Critically ill children and young people: do national Differences in access to Emergency Paediatric Intensive Care and care during Transport affect clinical outcomes and patient experience? The DEPICT study**

The structure of the provision of paediatric intensive care has changed in recent years. Prior to 1997, care of critically ill children was undertaken in 28 paediatric intensive care units (PICU), 125 adult intensive care units and 120 children's wards. However, expert opinion suggested centralisation of care and dedicated regional PICUs were set up alongside specialist retrieval team to transport critically ill children from general hospitals to PICUs.

Now, critically ill children can present to any one of 215 hospitals in the UK. Only 25 of these 215 hospitals have an on-site PICU and so children at the other 190 hospitals may need to be transferred to a PICU, at a median distance of 32 km. Transported children represent a third of PICU admissions and the use of a specialist team (paediatric intensive care retrieval team: PICRT) compared to a non-specialist team for inter-hospital transport improves odds of survival by 42%. The majority (~85%) of inter-hospital transfers are performed by specialist paediatric teams. However, we do not know whether differences in timeliness of access to paediatric intensive care and care delivered during stabilisation and transport by specialist teams matter in terms of clinical outcomes.

## 1.1 STUDY OBJECTIVES

The study objectives of the DEPICT Study are:

**Objective 1.1:** To perform a quantitative analysis using linked routinely collected audit data to study the association between timeliness of access to paediatric intensive care and clinical outcomes in a national cohort of critically ill children transported to PICU.

[Timeliness of access to intensive care will be measured by time to arrival at bedside after acceptance; time of referral to time of acceptance; time of referral to time of admission to PICU]

**Objective 1.2:** To perform a quantitative analysis using linked routinely collected audit data to study the association between care delivered by PICRTs and clinical outcomes in a national cohort of critically ill children transported to PICU. [We will study specific aspects of PICRT care such as team composition, interventions performed and critical incidents during transport].

**Objective 1.3a:** To explore, using qualitative methods (individual interviews and workshops) and questionnaires, the experiences and perspectives of a purposively sampled national cohort of parents of transported critically ill children.

**Objective 1.3b:** If and where feasible, to use innovative methods to explore the experiences of transported critically ill children.

**Objective 1.4:** To explore, using qualitative methods (individual interviews and workshops), the experiences and perspectives of a purposively sampled national cohort of clinicians from a range of settings (acute general hospitals, PICRTs and PICUs) and service managers/NHS commissioners.

**Objective 2.1:** To perform cost effectiveness analyses of PICRT provision for critically ill children, comparing different service models currently in use.

**Objective 2.2:** To use mathematical modelling and location allocation optimisation methods to explore whether alternative models of service delivery for PICU/PICRT services can improve clinical outcomes while remaining cost effective.

**Objective 2.3:** To synthesise study findings to inform the development of evidence-based national standards of care and information resources for families and clinicians.

## 1.2 STUDY DESIGN

Mixed methods study including a) retrospective quantitative analysis of linked routinely collected PICANet audit data, b) prospective qualitative study involving questionnaires and interviews of critically ill children transported to intensive care and their families, clinicians and managers, c) health economic analysis and d) mathematical modelling to evaluate whether alternative models of service delivery can improve clinical and cost effectiveness.

This statistical analysis plan relates to Objectives 1.1 and 1.2, which form the quantitative workstream.

## 2 APPROVALS

---

This table describes the required approvals for the DEPICT Study and provides the physical location for the evidence of it on the University of Leicester servers.

Approval required	Obtained?	
Data access and transfer approval from PICANet	Done	
Fair processing notice for PICANet	Done	
Fair processing notice for ICNARC	Done	
Data access and transfer approval from ICNARC	Done	
CAG approval for Section 251	Done	
REC approval	Done	
NIHR contract		
Study protocol		
NHS Digital application	Done	

FINAL

### 3 DATA SOURCES

---

#### 3.2 INTENSIVE CARE NATIONAL AUDIT AND RESEARCH (ICNARC)

Information from ICNARC will be provided on children who are admitted to adult intensive care units to receive care. The data request from ICNARC is for the following data items:

Unique CMP identifier (pseudoanonymised), NHS number (to allow the linkage, not to be provided to the research team), date of birth, sex, residential postcode (or IMD score), admitting unit, date of admission, source of admission, ICNARC physiology score, PRISM

score, date of discharge (or length of stay), vital status at discharge, discharge location, type and duration of organ support interventions provided (respiratory, cardiovascular, renal, neurological), location prior to admission.

Identifiable PICANet and ICNARC data including NHS number will be passed from the University of Leeds and ICNARC to NHS Digital to allow for linkage with ONS and HES data (see below). The data flow is described in the diagram.

### 3.3 DATA LINKAGE

The ICNARC and PICANet data sources will be linked with the following data sources:

#### **Office of National Statistics (ONS): linkage undertaken by NHS Digital**

Information extracted from death certificates will be provided by ONS.

As of May 2018 it is unclear if we will be able to obtain full ONS data and if not we will request derived information about 30-day, 90-day and 1-year mortality post-admission.

[figure not shown]
#### **Hospital Episodes Statistics (HES): linkage undertaken by NHS Digital**

Information from HES will be used to provide information about admissions via Accident & Emergency and to receive information about hospital care received in a non-paediatric intensive care environment (e.g. on a ward). This can be used to inform information about length of stay in other hospital environments; re-admission to hospital or other emergency care received.

#### **Admitted Patient Care (APC) and Emergency Department Dataset (EDDS), NHS Wales: linkage undertaken by NHS Wales Informatics Service**

The ethical approval and CAG approval to access the Welsh data have not yet been acquired (as at May 2018). When these have been obtained, data will be applied for. NHS Wales will only undertake linkage using NHS Number.

FLOW OF DATA IN THE DATA LINKAGE PART OF THE DEPICT STUDY

The DEPICT study, IRAS ID 218569

07/07/2017

Red boxes indicate transfers where personal data will be included; blue boxes indicate no personal data will be included in the transfer. All transfers will utilise secure transmission means.

## 4 DATA & DATA MANIPULATION

---

The data acquisition will follow these steps as outlined in the NHS Digital application:

- 1) Data flows to NHS Digital from the University of Leeds (PICANet) and ICNARC (Case Mix Programme) will each securely transfer a file to the NHS Digital Data Access Request Service (DARS). These files will contain person-identifiable information (NHS Number, sex, post code, date of birth) and unique study identifiers (PICANet: DEPICT Study Number; CMP: CMP identifier) required to perform the data linkage.
- 2) NHS Digital will identify common records between PICANet data and CMP data.
- 3) Data flow from NHS Digital will return linked HES and ONS mortality data for all individuals in the PICANet or ICNARC datasets to the University of Leicester - NHS Digital will supply a list of the study identifiers common to PICANet and CMP to University of Leicester - The unique study identifiers (DEPICT study number and CMP identifier) will be appended to the end of every episode record returned to the University of Leicester.
- 4) The team at the University of Leicester will securely transfer the list of DEPICT study numbers and CMP study identifiers to University of Leeds and ICNARC respectively. No HES or ONS data or personal identifiers will be transferred.
- 5) Data flow from University of Leeds (PICANet) and ICNARC (CMP) University of Leeds and ICNARC will provide admission level clinical data from their respective audits for the specific DEPICT and CMP identifiers to University of Leicester by means of secure transfer. No personal identifiers will be transferred.

Data acquisition from NHS Wales will follow a similar process and data flow.

### 4.1 INCLUSION/EXCLUSION

Data on all children ( $\leq 16$  years old) admitted to PICUs in the England and Wales from 2014 to 2016 following transport by a specialist team will be included. Transport events will be linked with the appropriate admission information and other longer-term outcome data. Some children will be transported and admitted more than once over this time period. Summary statistics will be produced for both admission and for the individual child, and analyses will be undertaken using both approaches and compared. For the analysis at child level, the admission closest to the final event will be used and a variable will be included to indicate if they had previous admissions to PICU.

Exclusions will be made for:

- Transport of adults (age  $>16$  years)
- Transport to an unknown location; no match between transport and admission event; transport performed by non-specialist team; transport performed by neonatal team.

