### 5.2 SUMMARY STATISTICS

Summary statistics will be presented to describe the population including:

- Number of children transferred, n (%)

- Age, mean (SD) and sex, n (%) of transported children
- Characteristics of the transports undertaken, n (%)
  - E.g. grade of team leader; care area of handover; operational times (median, range); interventions prior to or during transport, n (%)
- Interventions during or prior to transport conducted by the retrieval team, n (%)
  - E.g. intubation; CVC insertion; primary intraosseous access; arterial access; inotrope infusion; chest drain; ECMO; adverse events en route.
- Primary diagnosis reason, n (%)
  - E.g. respiratory; neurological; cardiovascular; infection; endocrine/metabolic; haematology/oncology; trauma; other
- Reason for admission, n (%)
  - E.g. bronchiolitis; seizure disorder; asthma; croup; postoperative; diabetic ketoacidosis
- PIM-2/PIM-3 predicted mortality risk, median and range
- PIM-2/PIM-3 predicted mortality risk categorised, n (%):
  - Grouped as <1; 1 to <5; 5 to <15; 15 to <30; 30-100.
- PaO2/FIO2 ratio, n (%)
  - Grouped as: <200; 201-300; >300
- Cardiac arrest before contact with transport team, n (%)
- Died in PICU; died within 30 days of admission to PICU; died within 90 days of admission; died within one year, n (%)
- Length of PICU stay, median numbers of days and range
- Information about daily interventions in the PICU, median days (range)

Whilst they will not form part of the main analysis, we will also report the number of children who die en route, and the median (range) time taken to reach their bedside by the transport team.

The differences between the transport teams in terms of their team composition, demographics they serve and facilities they have available will be described descriptively if possible.

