## 5.3 FORMAL STATISTICAL ANALYSES

### 5.3.1 Outcomes for all analyses

#### Primary outcome:

30-day mortality following PICU admission (following first admission) using data from the Office of National Statistics.

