#### Secondary outcomes to include:

a) Mortality at fixed time-points (PICU discharge, 90 days and 1 year following [first] PICU admission – data linked from ONS)

b) Number of PICU admissions during study period and time to readmission (if applicable)

- c) Length of stay in PICU (number of days from PICU admission to discharge, for each PICU admission)
- d) Resource use in PICU (number of days of invasive ventilation, vasoactive agent therapy, renal replacement therapy and extra-corporeal life support during PICU stay, for each PICU admission)
- e) Length of hospital stay linked to the first PICU admission (number of days from hospital admission to hospital discharge)
- f) Number of A&E attendances in the 12 months following discharge from the first PICU admission (using data from HES and NHS Wales)
- g) Hospital resource use (total number of days admitted to hospital) in the 12 months following discharge from the first PICU admission (using data from HES and NHS Wales)

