#### **Model 1: The impact on mortality due to timeliness of access to care in transported children**

Three time frames will be considered when investigating the outcome of mortality and timeliness of access to care:

- Time to arrival at bedside after acceptance (we will investigate this first)

- Time of referral to time of acceptance
- Time of referral to time of admission to PICU

A variable to represent timeliness of access to care will be included to indicate if the transport was made in the desired time frame (e.g. continuous time to arrival or dichotomised using any targets: <3 hours: yes/no) or in groupings of 30 mins (0-30 mins; 30-60 mins; 60-90 mins etc.). Other confounders will be identified and included (see Section 5.3.2). If reasons for delay want to be investigated then the PICANet free text comments fields will be interrogated.

Differences which may exist between the transport teams will be accounted for in all analyses of the primary outcome either via use of logistic mixed models (random effect term for transport team) or logistic models with robust standard errors to account for clustering within transport services. Both of these approaches will give very similar (although not identical) results in terms of the coefficients. The model fit will be assessed to see if consideration of transport team improves the model fit via use of the AIC. If differences between transport teams are of direct interest, a categorical term to indicate the transport team will also be included within the model.

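### The admission-level mortality analysis inherits a clock that starts at the child's first admission, so some deaths soon after a later transport are coded as survivals, and dependence between a child's rows is only partly covered

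*SAP*

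**What the plan says.** SAP section 4.1 states that "Some children will be transported and admitted more than once over this time period" and that "Summary statistics will be produced for both admission and for the individual child, and analyses will be undertaken using both approaches and compared". So there is one analysis with a row per admission and another with a row per child.

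Section 5.3.1, whose heading covers all analyses, gives the primary outcome as "30-day mortality following PICU admission (following first admission) using data from the Office of National Statistics". Secondary outcome (a) follows the same clock: "Mortality at fixed time-points (PICU discharge, 90 days and 1 year following [first] PICU admission". Outcomes (c) and (d) do not. PICU length of stay, for instance, is the "number of days from PICU admission to discharge, for each PICU admission". The authors thus distinguished the two bases and put mortality on the first-admission one.

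Elsewhere the first-admission restriction is absent. Section 5.2 tabulates children who "died within 30 days of admission to PICU", and section 4.2 gives the 7% planning figure for transported PICU admissions generally.

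On dependence, Model 1 in section 5.3.3 offers either a random effect for transport team or "logistic models with robust standard errors to account for clustering within transport services". Neither option has a term for the child. Section 4.2 admits that its one-child-per-transport assumption is untrue, but no modelling provision follows.

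**The concern.** In the admission-level model the exposure varies by row: each transport has its own delay. The stated outcome does not vary by row, because it is fixed by the child's first admission. A later transport that is soon followed by death can therefore enter the model as a survival, with its delay scored against the wrong result. Conversely, a death within 30 days of the first admission is carried onto every row of that child.

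Two things are at stake. The first is the primary outcome in one of the two planned analyses, and hence the meaning of comparing them: a difference between levels could reflect different endpoints rather than sensitivity to repeat admissions. The second is the confidence intervals. Section 5.3.6 reports these instead of p-values, and they may be too narrow if rows from the same child are treated as independent.

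**Working it through.** **1. The plan's own figures.** From section 4.2: 15,000 × 0.85 = 12,750 transports under 3 hours and 15,000 × 0.15 = 2,250 over 3 hours, as stated. Expected death records are 15,000 × 0.07 = 1,050. Power for 7% against 4% with this split, at a two-sided 5% level (assumed, as none is stated), is 99.997% with the 4% in the over-3-hour group and 99.988% with the 7% there. If 20% of transports were repeats and only one per child were kept (12,000 rows), power would still exceed 99.9%. The issue is outcome definition and dependence, not power.

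**2. The two clocks on illustrative children with two transported admissions.**

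| Admissions and death | First-admission clock (5.3.1) | Each row's own clock |
|---|---|---|
| January 2014 and June 2015; death 3 days after the second | survivor on both rows | row 1 survivor, row 2 death |
| Days 0 and 20; death on day 40 | survivor on both rows | row 1 survivor, row 2 death |
| Days 0 and 20; death on day 25 | death on both rows | death on both rows |

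The first two lines show the miscoding. The third shows that one death can appear on two rows under either clock when admissions are close together. That overlap widens for the 90-day and 1-year outcomes. Death by PICU discharge, taken per admission, cannot be counted twice.

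**3. How many deaths.** The SAP gives neither the share of transports that are repeats nor the gaps between them, so both are assumptions:

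- *r*, the share of the 15,000 transports that are repeats: 5–20%.
- *q*, the share of repeats within 30 days of the preceding admission: 10–50%.
- 30-day mortality after any admission: 7% (the section 4.2 figure, assumed to apply to repeats).

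A repeat more than 30 days after the preceding admission is necessarily more than 30 days after the first, so every death following it is missed by the first-admission clock.

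Deaths coded as survivals ≥ 15,000 × *r* × 0.07 × (1 − *q*):

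- *r* = 5%, *q* = 50%: 15,000 × 0.05 × 0.07 × 0.5 = 26 (2.5% of 1,050)
- *r* = 10%, *q* = 30%: 15,000 × 0.10 × 0.07 × 0.7 = 73.5, about 74 (7.0%)
- *r* = 20%, *q* = 10%: 15,000 × 0.20 × 0.07 × 0.9 = 189 (18.0%)

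These are lower bounds, because cases like the second line of the table add to them.

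Duplicate death records under a per-row clock ≤ 15,000 × *r* × 0.07 × *q*, if each repeat has at most one earlier admission within 30 days. This runs from 5 (*r* = 5%, *q* = 10%) to 105 (*r* = 20%, *q* = 50%), or 0.5–10.0% of 1,050.

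**4. Effect on the odds ratio if miscoding is unrelated to delay.** With 7% against 4%, the odds ratio is (0.07/0.93)/(0.04/0.96) = 1.81. Losing 10% of deaths in both groups gives 6.3% against 3.6%, odds ratio 1.80. Losing 20% gives 5.6% against 3.2%, odds ratio 1.79. All print as 1.8 at the one decimal set in section 5.3.6. A material shift needs the miscoding to differ between short and long delays.

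**5. Dependence.** Standard errors robust to clustering by service allow for correlation among all rows within a service, and so among a child's rows when one service made every transport. They do not cover a child moved by different services. The random-effect option models correlation shared by a team's patients but not the extra correlation within a child. For outcomes (c) and (d), which have one record per admission, section 5.3.3 names no child-level provision either.

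**The case against.** A reader might infer that the admission-level analysis has no valid mortality outcome. That goes too far. Death within 30 days of each admission is a legitimate endpoint, and sections 4.2 and 5.2 already use it. The fault is that section 5.3.1 states a different clock for all analyses.

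A reader might also infer that a per-row clock is invalid because it counts a death twice. With admissions on days 0 and 20 and death on day 25, both rows truthfully record a death within 30 days. What remains is a question of attribution and dependence, and only for closely spaced admissions.

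The strongest counter-argument concerns consequence: miscoding unrelated to delay barely moves the odds ratio, as shown in the working. That stands. The documents do not support a claim that the timeliness estimate is biased by a known amount or in a known direction.

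Two further mitigations are fair but partial. Service-level robust errors cover children always moved by one service, and previous admission to intensive care is among the candidate confounders in section 5.3.2. Neither corrects an outcome coded from the wrong admission, and a covariate for previous admission does not model within-child correlation.

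Finally, the child-level rule, under which "For the analysis at child level, the admission closest to the final event will be used", also conflicts with the first-admission clock. That is a related contradiction. It does not remove this one.

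**Conclusion.** The point holds as a conflict within the SAP. Section 4.1 commits to an analysis with repeat rows, while section 5.3.1 fixes mortality from the first admission for all analyses. Followed literally, this codes a death more than 30 days after the first admission as survival even on the row for the transport that preceded it by days. It also disagrees with the per-admission mortality in sections 4.2 and 5.2. Within-child dependence is unmodelled under the random-effect option and, under either option, for children moved by different services.

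The size is unknown. The range of at least about 26–189 miscoded deaths out of about 1,050 rests on assumed repeat shares of 5–20%, assumed close spacing of 10–50%, and 7% mortality after every admission. Whether the odds ratio changes materially depends on whether miscoding differs by delay, which the documents cannot settle. The wording should be corrected before analysis because the rule as written gives wrong outcomes for some rows and the intervals may be too narrow.

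**What to change.** 1. In section 5.3.1, state that in the admission-level analysis 30-day, 90-day and 1-year mortality run from that row's own PICU admission.
2. In section 5.3.3, account for repeated admissions of the same child in the admission-level models, by child-level clustering or a child random effect, alongside the provision for transport team. Apply this to outcomes (c) and (d) as well. A child may be moved by more than one service, so children should not be assumed to be nested within teams.
3. In section 5.3.5, add a sensitivity analysis in which a death falling within the window of two admissions is attributed only to the last one. This belongs in a sensitivity analysis rather than the main model, because it codes the earlier row as a survival although the child died within its window.

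The cost is a few sentences of SAP text, modest extra modelling and slightly wider intervals. No new data are needed if death dates are supplied. Section 3.3 warns that only derived 30-day, 90-day and 1-year mortality may be available. In that case the request should ask for these indicators for every transported admission, and for enough detail to identify overlapping windows.

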### 4.2 SAMPLE SIZE

PICANet data from 2014/15 indicates that the 30-day mortality rate for transported PICU admissions is approximately 7% and that transport teams reach critically ill children within 3 hours of referral acceptance in 85% of cases (the current target). We anticipate a sample of

15,000 transports over the three year time window of the DEPICT Study. Of the 15,000 transports we anticipate that approximately 12,750 (85%) will be made in less than 3 hours. The remaining 2,250 (15%) will be made in more than 3 hours. We have adequate power to detect a 3 percentage point reduction in mortality (7% to 4%). This sample is assuming that each transport and admission is a separate child, when in reality a single child may contribute multiple transports.

Adjustments will be made using the 'rule of thumb' of at least ten events per adjustment. For example, if we observed 400 deaths, we would make no more than 40 adjustments. However, we will work to ensure statistical parsimony by keeping the model as simple as practical.

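### The child-level analysis and the mortality outcomes use different index admissions; selecting the last admission inflates absolute risk and can bias the timeliness odds ratio

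*SAP*

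**What the plan says.** Section 4.1 recognises repeat transports: "Some children will be transported and admitted more than once over this time period". It plans both an admission-level and a child-level analysis, and "analyses will be undertaken using both approaches and compared". Neither is named as the main one. For the child-level analysis the record is fixed by this rule: "For the analysis at child level, the admission closest to the final event will be used". In addition, "a variable will be included to indicate if they had previous admissions to PICU".

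Section 5.3.1 defines the primary outcome as "30-day mortality following PICU admission (following first admission) using data from the Office of National Statistics". The later mortality outcomes have the same origin: "Mortality at fixed time-points (PICU discharge, 90 days and 1 year following [first] PICU admission". Length of hospital stay, A&E attendances and hospital days over the following year are also tied to the first PICU admission.

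No section says what the final event is, or how a record chosen by it relates to an outcome that starts at the first admission.

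**The concern.** The two rules agree for a child with one transport and conflict for a child with several. There are two ways to carry them out, and neither is sound.

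- **Both rules taken literally.** Timeliness and confounders come from the last admission, and the outcome from the first. A child transported again more than 30 days after the first admission has, by definition, survived 30 days from it. That child is coded as a survivor against the timeliness of a later journey, even if death follows that journey. Section 5.3.3 repeats the models for the secondary outcomes, so an exposure could also be measured after the outcome it should explain, such as time to readmission.
- **Last admission used for both.** A transport is dropped only because the child lived to be transported again. Selection into the analysis then depends on what happened after the exposure.

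This record underlies Models 1 and 2 for the primary outcome. Two analysts following the SAP could build different child-level datasets. Absolute risks are also at stake, because section 5.3.6 promises predicted probabilities.

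**Working it through.** **The plan's own figures.** Section 4.2 gives 15,000 transports, of which 85% are reached within 3 hours: 15,000 × 0.85 = 12,750 and 15,000 × 0.15 = 2,250, as stated. The "30-day mortality rate for transported PICU admissions is approximately 7" per cent, so about 15,000 × 0.07 = 1,050 deaths.

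**Assumptions.** The SAP gives no repeat-transport rate. Let r be the probability that a survivor is transported again, taken as 10% or 20%. Let the risk ratio (RR) for re-transport after late arrival be 0.5 to 2.0. Death has probability p = 0.07 per admission. Subscript 0 is on time and 1 is late.

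**Absolute risk when the last record is kept.** A first transport is retained if the child dies or survives without re-transport, so its mortality is p / [p + (1 − p)(1 − r)]. If r recurs after each transport, the same expression gives deaths per child.

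- r = 0.10: 0.07 / (0.07 + 0.93 × 0.90) = 0.07 / 0.907 = 7.7%
- r = 0.20: 0.07 / (0.07 + 0.93 × 0.80) = 0.07 / 0.814 = 8.6%

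These correspond to 1 / 0.907 = 1.10 and 1 / 0.814 = 1.23 transports per child.

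**Odds ratio when there is no true effect.** The odds of death among retained first transports are p / [(1 − p)(1 − r)]. With the same p in both groups, the odds ratio, late versus on time, is (1 − r0) / (1 − r1). This was compared with a simulation of 3,000,000 children per scenario, 15% of them late.

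| r0 | RR | r1 | (1 − r0)/(1 − r1) | Simulated, last record |
|---|---|---|---|---|
| 0.10 | 0.5 | 0.05 | 0.947 | 0.945 |
| 0.10 | 1.0 | 0.10 | 1.000 | 0.994 |
| 0.10 | 1.5 | 0.15 | 1.059 | 1.058 |
| 0.10 | 2.0 | 0.20 | 1.125 | 1.122 |
| 0.20 | 0.5 | 0.10 | 0.889 | 0.889 |
| 0.20 | 1.0 | 0.20 | 1.000 | 0.996 |
| 0.20 | 1.5 | 0.30 | 1.143 | 1.139 |
| 0.20 | 2.0 | 0.40 | 1.333 | 1.334 |

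**Does the previous-admission indicator help?** Mantel-Haenszel stratification on previous admission gave the same simulated values to three decimals. The reason is that the selection also acts among children with no earlier admission: those who survived and were transported again have left that stratum.

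**Literal pairing.** Last-admission exposure with the first-admission outcome gave odds ratios of 0.89 to 1.32 under no true effect.

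**With a true odds ratio of 1.8.** The last record gave 1.60 to 2.41 across the same scenarios. The first admission, and all admissions together, each gave about 1.81.

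**The case against.** The study team could say that the rule keeps each death next to the care that preceded it, and that the admission-level analysis provides a check. Part of this stands. The admission-level analysis drops no record because of later survival, and in the simulation it recovered the true odds ratio. The comparison could therefore expose a selection effect. It would not show which child-level dataset was intended, and an outcome defined from the first admission does not define the outcome of a repeat admission.

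Several stronger readings are tempting, but the SAP does not support them:

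- **That the rule necessarily biases the timeliness odds ratio.** It does not when re-transport is unrelated to timeliness (0.99 to 1.00 simulated). Frailty that drives both death and readmission, but is unrelated to lateness, leaves it almost unchanged (1.74 against 1.75). Nothing in the SAP shows that re-transport depends on timeliness.
- **That bias follows if first and repeat journeys differ in timeliness.** With re-transport independent of timeliness and late arrival of 15% at first transport and 7.5% to 30% at repeat, the crude odds ratio was 0.97 to 1.02. Stratified on previous admission it was 0.99 to 1.00, so the planned indicator handles this route.
- **That every discarded transport was survived.** A child transported twice within 30 days who then dies contributes a 30-day death to both transports. The inflated mortality figures are therefore upper bounds for their assumed rates. They also partly reflect the move from a per-transport to a per-child denominator.
- **That the first PICU admission may have no transport exposure.** Section 4.1 restricts the cohort to admissions after specialist-team transport, so the natural reading is the first admission within that cohort. The wording could be tighter, but this is not a separate defect.

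**Conclusion.** The contradiction over the index admission is in the text and needs no assumption: section 4.1 and section 5.3.1 name different admissions for the same child, and the final event is undefined.

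The consequences are conditional. Keeping the last record raises crude 30-day mortality, and with it the predicted probabilities, from 7.0% to at most about 7.7% to 8.6% if 10% to 20% of survivors are transported again. The odds ratio is distorted only if re-transport depends on timeliness, or on unadjusted factors tied to it, and the distortion can go either way. With no true effect it is about 1.06 to 1.14 at a risk ratio of 1.5, and below 1 if late arrival goes with less re-transport. The actual size cannot be found from the SAP.

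**What to change.** In section 4.1, delete the rule that selects the admission by its closeness to the final event, and state instead:

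- The child-level index is the first specialist-team transport linked to a PICU admission in 2014-2016.
- Exposure, covariates and the 30-day, 90-day and 1-year clocks all come from that admission.
- Previous PICU admission is coded by look-back from the index only.

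This agrees with section 5.3.1 as it stands. In the simulation the first-admission index recovered the odds ratio (1.00 under no effect, 1.81 for a true 1.8).

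Keep the admission-level analysis for comparison. Time each admission's outcome from that admission, and use standard errors that allow for repeat transports of the same child; section 5.3.3 currently mentions only clustering by transport service. Which analysis leads is for the study team to state. The correction does not require the admission-level one to be ranked lower.

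The cost is a wording change and a simple rule in the data build. The downside is that deaths after later transports count only in the admission-level analysis, unless they fall within the first admission's outcome window.
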